3.12. Analysis of other outcomes

Time-to-event outcomes will be analysed using a Cox proportional hazards model, with, if necessary, baseline covariate adjustment in case of unexpected differences in baseline descriptive statistics. The estimated treatment effect will be presented in the form of hazard ratios with 95% confidence intervals. Kaplan-Meier plots will be used to present the pattern of events per treatment group over the follow-up period. The assumption of proportional hazards will be checked using statistical tests and graphical diagnostics based on the Schoenfeld residuals.

The exploratory safety endpoint will be assessed using a unmatched win ratio approach (16). Patients from the liberal fluid intake arm will be paired with every single patient from the standard fluid restriction arm. For each pair the better clinical outcome will be determined in the following sequential criteria and will stop after either patient has shown profit.

A 'win' is defined as the patient in the liberal fluid intake arm has the better outcome compared to the patient in the standard fluid restriction group. A 'loss' is defined in the opposite manner.

- 1. Death within 6 months follow-up
 - a. Death is worse than no death
 - b. Tied, if not possible to determine
- 2. HF hospitalisations within 6 months follow-up
 - a. More HF hospitalisations is worse
 - b. Tied, if not possible to determine
- 3. Requirement of iv-loop diuretics within 6 months follow-up
 - a. More events is worse
 - b. Tied, if not possible to determine
- 4. All-cause hospitalisation within 6 months follow-up
 - a. More all-cause hospitalisations is worse
 - b. Tied, if not possible to determine

The win ratio is: total number of wins / total number of losses.

The win difference is: percentage of wins minus percentage of loses.

4. Prespecified subanalyses

All patient characteristics of the prespecified subanalyses listed below will be presented in accordance with '3.7 Patient characteristics and baseline comparisons' of this document, unless stated otherwise.

Change of fluid management analysis

Aim:

- 1. To investigate the effect of liberal fluid intake versus fluid restriction in the subgroup of patients who were prescribed a fluid restriction prior to randomisation on the primary, (key) secondary and explorative endpoints
- 2. To investigate the effect of increased fluid intake in the subgroup of patients who were prescribed a fluid restriction at baseline on the primary, (key) secondary and explorative endpoints

Analysis:

- 1. Population: Patients who were prescribed any form of fluid restriction prior to randomisation will be included.
- 2. Population: Patients who were prescribed any form of fluid restriction prior to randomisation and who were randomised to liberal fluid intake. Patients will be divided into two groups for analysis based on their average fluid intake at week 6 (less or more than 2L).
- 3. Population: Patients who were prescribed any form of fluid restriction prior to randomisation. Patients will be divided into three groups:
 - a. Randomised to fluid restriction.
 - b. Randomised to liberal fluid intake and a fluid intake of less than 2L based on their average fluid intake at week 6.
 - c. Randomised to liberal fluid intake and a fluid intake of more than 2L based on their average fluid intake at week 6.

The analysis on the primary, (key) secondary and exploratory endpoints will be performed as described in '3.10 Analysis of the primary outcome', '3.11. Analysis of the secondary outcomes' and '3.12 Analysis of other outcomes'.

Thirst and QoL analysis

Aim:

- 1. To investigate the relationship between thirst and QoL.
- 2. To investigate the effect of thirst status on the effect of liberal fluid intake versus fluid restriction.

Analyses:

- 1. Population: All patients with completed KCCQ and TDS-HF
 - a. At baseline;
 - Correlation between baseline KCCQ-OSS (and subdomains) and TDS-HF
 - A multiple regression analysis between baseline KCCQ-OSS (and subdomains) and TDS-HF.
 - b. Follow-up;
 - Correlation between the change in KCCQ-OSS and subdomains and TDS-HF per randomisation arm.
- 2. Population: Patients will be categorized into based on the TDS-HF:
 - a. No thirst (score = 8).
 - b. Minimal to moderate thirsty (score = 9 to 24).
 - c. Moderate to very thirsty (score = 25 to 40).

The analysis on the primary and secondary endpoints will be performed as described in '3.10 Analysis of the primary outcome' and '3.11. Analysis of the secondary outcomes'. Baseline characteristics will include all subdomains of the KCCQ.

In depth analysis

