# 6. Based on prior experience, do the authors have a sense of cross-over rates (re: Discontinuation of study treatment section) between study arms? Why wasn't cross-over accounted for in the sample size calculation?

During the design phase of study we expected the rates of discontinuation of study treatment to be very low. In our experience, participants are highly motivated to adhere to the study protocol. As expected, most patients already adhere to the control therapy and are excited to particate in the interventional group. The drop-out rate of the control group is very low and there are, till further notice, no drop-outs in the interventional group. Our objective is to study the effect of a fluid advice in a real-world situation and a pragmatic design was chosen in which the cross-over rate was assumed neglectable. In addition, because the primary analysis is based on the intention-to-treat population we are essentially specifying a treatment policy estimand approach for the primary analysis, in which outcomes are measured regardless of whether patients divert from their advised fluid intake or not.

7. The authors acknowledged in the Limitations that patient-reported fluid intake at week 6 may not be reliable and yet this will form the basis of the per-protocol analysis. I worry about the utility of the per-protocol analysis if there will be misclassification on adherence. Is it feasible to record fluid intake daily? Furthermore, regardless of misclassification, per-protocol is a biased analysis and the authors may wish to consider causal inference methods (e.g., instrumental variable analysis) to address non-adherence.

We agree with the reviewer that the true fluid intake cannot be determined with full certainty. In that regard, we feel it is important to state that our primary analysis is based on an intention-to-treat principle. Our per-protocol analysis is only considered as an additional supporting analysis, but is indeed quite limited due to uncertainty on actual fluid intake.

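### The win ratio has no rule for pairs observed for different lengths of time within 6 months and ignores when death occurs, so less observation can be scored as the better outcome

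*SAP*

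**What the plan says.** SAP section 3.12 assesses the exploratory safety endpoint by an unmatched win ratio. Each pair passes through four tiers until one of them separates the two patients:

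1. Death: "Death is worse than no death". The date of death plays no part.
2. HF admissions: "More HF hospitalisations is worse".
3. Intravenous loop diuretics: "More events is worse".
4. Admissions for any cause: "More all-cause hospitalisations is worse".

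Every tier is limited to the same nominal window, as in "HF hospitalisations within 6 months follow-up", and every tier ends with "Tied, if not possible to determine". The SAP does not say what makes a tier impossible to determine, or what to do when one patient of a pair was observed for less than 6 months.

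The plan does expect incomplete data. Section 2.6 allows for 10% drop-out, and section 3.6 will report the number lost to follow-up. The same section 3.12 also analyses time-to-event outcomes by Cox models and Kaplan-Meier plots.

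**The concern.** A raw count depends on how long the patient was watched. If both patients complete 6 months, the comparison is fair. If one of them leaves or dies early, fewer events can be recorded for that patient, and the rule can treat the missing time as good outcome. Two results follow from the wording alone:

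- A patient lost alive at month 2 with no recorded event wins against one followed to month 6 who had one HF admission, or who died at month 5.
- If both patients died, tier 1 ties. The patient who died earlier had less time to be admitted, and can win at tiers 2 to 4.

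At stake is the reading of one safety comparison of the investigational advice. The change-of-fluid-management subanalysis in SAP section 4 refers back to section 3.12 for the exploratory endpoints, so the gap carries over to it. Section 3.4 says that the analysis is done with allocation known after database lock, so the handling of incomplete pairs should be fixed beforehand.

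**Working it through.** **Arm size.** The plan states no event rate, power or expected value for the win ratio. The only plan figure used here is the number of patients. From SAP section 2.6: difference 2.5, SD 20, correlation 0.88, two-sided alpha 0.05, power 80%.

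n per arm = 2 × (1.960 + 0.842)² × 20² × (1 − 0.88²) / 2.5² = 2 × 7.849 × 90.24 / 6.25 = 226.6, so 227 per arm and 454 in total, as stated. Then 454 / 0.9 = 504.4, which gives 505, or 506 for equal arms, as stated. That is 253 per arm and 253 × 253 = 64,009 pairs.

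**Simulation with no treatment effect.** 253 per arm and 300 simulated trials per row. All event rates and loss patterns are assumptions; the documents give none.

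- Scenario A: 6-month death 2%; mean events per patient 0.04 (HF admission), 0.04 (intravenous diuretic), 0.15 (all-cause admission).
- Scenario B: death 5%; means 0.08, 0.06, 0.25.
- Event rates vary between patients (gamma frailty, variance 1). Loss occurs at a uniform time within the 6 months and is unrelated to outcome.
- SAP rule: death yes/no, then observed counts, without using the tie clause for incomplete follow-up.
- Shared rule: order of death and counts up to the shorter follow-up of the pair.

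| Scenario | Loss, liberal / restriction | Win ratio, SAP rule | Win ratio, shared rule | SAP / shared |
|---|---|---|---|---|
| A | 0% / 0% | 0.990 | 0.991 | 1.00 |
| A | 10% / 10% | 0.991 | 0.991 | 1.00 |
| A | 15% / 5% | 1.045 | 0.989 | 1.057 |
| A | 5% / 15% | 0.937 | 0.990 | 0.946 |
| A | 20% / 0% | 1.105 | 0.989 | 1.117 |
| B | 0% / 0% | 1.005 | 1.005 | 1.00 |
| B | 10% / 10% | 1.002 | 1.001 | 1.00 |
| B | 15% / 5% | 1.059 | 0.999 | 1.060 |
| B | 5% / 15% | 0.944 | 1.000 | 0.944 |
| B | 20% / 0% | 1.127 | 1.001 | 1.126 |

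The two rules are applied to the same simulated trials, so the last column isolates the effect of the rule. A 10-point imbalance moves the win ratio by 5.4% to 6.0%, and a 20-point imbalance by about 12% to 13%, always towards the arm with more loss. With 10% loss in each arm the rules classify 1.73% (A) or 2.79% (B) of pairs differently, but the false wins and false losses cancel.

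A second simulation with other assumed rates (death 2%, HF admission 5%, intravenous diuretics 4%, all-cause admission 20%) agrees. With no loss in the liberal arm and 5% or 10% in the restriction arm, the win ratio is 0.97 or 0.95 as written, against 1.00 or 1.01 over shared follow-up.

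**Against chance variation.** The second simulation has a Monte Carlo standard error of about 0.01 for the log win ratio over 300 trials, so the SD for one trial is about 0.01 × √300 = 0.17. The 95% range with no effect is then about exp(±1.96 × 0.173) = 0.71 to 1.40. A shift to 0.944 is ln(0.944) = −0.058, about one third of an SD. The 0.99 values in scenario A are within Monte Carlo error.

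**Both died (rows with no loss).** Scenario A: 0.0389% of 64,009 = 24.9 pairs, and the earlier death wins in 11.6% of them, or 2.9 pairs. Scenario B: 0.2592% = 165.9 pairs and 17.6%, or about 29 pairs.

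**The case against.** The strongest defence has four parts.

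**The window.** A reader might infer that patients are compared with no common follow-up at all. The documents do not support that. Each tier is limited to 6 months, so all pairs of completers are compared over equal time. The gap concerns incomplete pairs only.

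**The tie clause.** The count of interest is a 6-month count, and for a patient lost at month 2 it is unknown. "Tied, if not possible to determine" can fairly be read as making such a pair a tie. This stands as a possible reading, but the SAP does not choose it, and the readings differ in effect. If 10% were lost in each arm, 1 − 0.9 × 0.9 = 19% of pairs would include an incomplete patient and could be set to a tie (many would tie anyway), whatever had been observed before the loss.

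**The direction.** A reader might infer a bias against liberal intake from the protocol's rebuttal letter (reply to major concern 6), which says "there are, till further notice, no drop-outs in the interventional group". That does not follow. The same reply calls drop-out in the control group very low, and the statement is provisional. It answers a question on cross-over and discontinuation of study treatment, and adds that outcomes are measured whether or not patients keep to the advice. Stopping the advice need not end event follow-up. The 10% in SAP section 2.6 is an overall allowance for patients evaluable on the KCCQ, not an arm-specific rate of lost event data.

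**The weight.** The analysis is exploratory, and the Cox models handle censoring for first events. Both points are right. They limit the importance of the gap but do not close it in the win ratio itself.

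**Conclusion.** The point holds in a limited form. Within its 6-month window the win ratio has no rule for unequal observed time, leaves the tie clause undefined, and ignores the order of two deaths. Taken literally, shorter observation or an earlier death can be scored as the better outcome.

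Net bias needs loss of event follow-up that differs between arms, and it can go either way. Under the assumed rates it is about 5% to 6% for a 10-point imbalance, small beside chance variation, and not visible with equal loss. Nothing in the documents establishes such an imbalance or its direction. The simulations assume loss unrelated to outcome; informative loss was not examined. The both-died part is very small. This is a cheap improvement to an exploratory safety analysis and leaves the primary and key secondary tests untouched.

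**What to change.** In SAP section 3.12, replace the open tie clause with a rule based on shared follow-up:

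- For each pair, shared follow-up is the shorter of the two observed times, up to 6 months.
- Tier 1: the patient known to have died first within shared follow-up loses.
- Tiers 2 to 4: compare the numbers of events within shared follow-up.
- A tier is tied only if it does not separate the pair within shared follow-up; the pair then moves to the next tier.

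State that the same rule applies where SAP section 4 uses section 3.12. Reporting the time of end of event follow-up by arm would show whether the issue mattered.

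The cost is SAP wording, a small change to the pairwise code and a few more tied pairs, because events after the shorter follow-up no longer count. First-event and censoring dates are already needed for the Cox models; dates of repeat events are needed too, and their availability should be confirmed. A further tie-break on time to first event is optional: it would change the hierarchy and is not needed for this repair.

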3.7. Patient characteristics and baseline comparisons

Baseline descriptive statistics will be presented both in text (for certain characteristics) and in table. Categorical variables will be presented with numbers (percentages) and compared using a Chi-squared test or Fisher exact test, whichever is appropriate. Continuous variables will be assessed for normal distribution and reported as means (standard deviation) or medians (interquartile range), whichever is appropriate. Baseline characteristics will be presented by randomisation group and for the overall population.

The following characteristics will be presented:

- Age
- Sex at birth
- Race
- Baseline KCCQ-OSS
- Baseline TDS-HF
- NYHA Class
- Ejection fraction (percentage, HFrEF, HFpEF)
- Pathogenesis of heart failure (ischemic, dilating, hypertension, valvular, drug-induced, other, unknown)
- Heart failure duration
- Medical history (current fluid management, atrial fibrillation/flutter, BMI, COPD, DM, hypertension, currently smoking)
- Laboratory values (haemoglobin, sodium, potassium, urea, eGFR, NT-proBNP, osmolality)
- Concomitant therapies (see below)

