Appendix 1: Proposed tables and figures

All tables and figures are drafts and will not necessarily be included in the final papers in this form.

1. Study disposition figure

2. Baseline characteristics table

	Total (N = ***)	Fluid restriction (N = ***)	Liberal fluid intake (N = ***)
Age, years			
Male			
White†			
Quality of life			
KCCQ-OSS			
TDS-HF			
EQ-5D-5L			
NYHA functional class			
II			
III			
LVEF			
%			
HFrEF			
HFmrEF			
HFpEF			
Pathogenesis HF			
Ischemic			
Dilating			
Hypertension			
Valvular			
Drug-induced Other			
Unknown			
HF duration, years			
Fluid management Fluid restriction of 1L			
Fluid restriction of 1.5L			
Fluid restriction of 1.5 to 2L			
Fluid restriction of 1.5 to 2.			
Liberal fluid intake			
Other			
HF treatment			
ACEi or ARB			
ARNI			
β-blocker			
Digoxin			
MRA			
SGLT2i			
Loop diuretics			
Thiazides			
GDMT score‡			
ICD			
CRT			

Medical history

Atrial fibrillation or flutter

BMI, kg/m²

COPD

DM

Hypertension

Currently smoking

Laboratory results

Haemoglobin, mmol/l

Sodium, mmol/l

Potassium, mmol/l

Urea, mmol/l

eGFR, ml/min/1.73m²

Nt-proBNP, pg/ml

Osmolality, mosm/kg

3. Outcomes

Table: 'Primary and secondary outcomes.'

	Fluid restriction (N = ***)	Liberal fluid intake (N = ***)	P value
Primary outcome			
KCCQ-OSS			
Key secondary outcome			
TDS-HF			
Other secondary outcome			
KCCQ-CSS			
KCCQ-TSS			
KCCQ-PLS			
KCCQ-QoL			
KCCQ-SBS			
KCCQ-SES			
KCCQ-SFS			
KCCQ-SLS			
KCCQ-SSS			
KCCQ-OSS (-5 to +5)			
KCCQ-OSS (-5 or less)			
KCCQ-OSS (+5 or more)			
EQ-5D-5L			
Reported fluid intake			
Safety			
Death			
All-cause hospitalisation			
IV-loop diuretics usage			
Composite of the above			
Acute kidney injury†			
Values are mean ± SD or median (int	erquartile range)		

alues are mean ± SD or median (interquartile range)

EQ-5D-5L = European Quality of Life Five Dimensions Five Levels questionnaire; KCCQ = Kansas City Cardiomyopathy Questionnaire; -CSS = Clinical Summary Score; -TSS = Total Symptom Score; -OSS = Overall Summary Score; -PLS = Physical Limitation Score; -QoL = Quality of Life; -SBS = Symptom Burden Score; -SES = Self-Efficacy Score; -SFS = Symptom Frequency Score; -SLS = Social Limitation Score; -SSS = Symptom Stability Score; IV = intravenous; TDS-HF = Thirst Distress Scale for patients with HF;

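### The sub-analysis of increased fluid intake compares self-chosen week-6 intake below and above 2 L: it does not measure the increase, and it should be reported as an association adjusted for the prior limit

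*SAP*

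**What the plan says.** All of this is in SAP section 4, under the change of fluid management analysis, unless another place is named.

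- **Aim 2:** "To investigate the effect of increased fluid intake in the subgroup of patients who were prescribed a fluid restriction at baseline", on the primary, secondary and exploratory endpoints.
- **Population of Analysis 2:** "Patients who were prescribed any form of fluid restriction prior to randomisation and who were randomised to liberal fluid intake".
- **Grouping in Analysis 2:** "Patients will be divided into two groups for analysis based on their average fluid intake at week 6 (less or more than 2L". Analysis 3 uses the same line; its third group is "Randomised to liberal fluid intake and a fluid intake of more than 2L based on their average fluid intake at week 6".
- **Prior limits:** the baseline table in SAP Appendix 1 has rows for "Fluid restriction of 1L", for 1.5 L, and for "Fluid restriction of 1.5 to 2L". There is also a row for other arrangements, and one row is cut off in the text available.
- **Fluid variable at baseline:** SAP 3.7 lists "Medical history (current fluid management, atrial fibrillation/flutter, BMI, COPD, DM, hypertension, currently smoking". This is the management advised. No measured baseline intake is listed.
- **Intervention:** under SAP 2.4 the liberal arm has no target volume; patients drink what they wish.
- **Model:** the sub-analysis refers back to SAP 3.10, 3.11 and 3.12. SAP 3.10.1 is an ANCOVA with baseline quality of life as covariate, and 3.10.2 plans no adjusted analysis.

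**The concern.** The aim and the analysis address different quantities. An increase is a change from a starting point, and the starting points differ between patients. A fixed 2 L line ignores that.

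The two groups are also formed by behaviour after randomisation within a single arm, so randomisation does not balance them. Thirst, body size, diuretic dose and congestion plausibly influence how much a patient drinks, and they may also relate to quality of life, NT-proBNP and clinical events. An ANCOVA with baseline quality of life alone does not deal with this.

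At stake is a published statement that drinking more has an effect, helpful or harmful, resting on a confounded comparison. The endpoints covered include safety.

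**Working it through.** The plan gives no calculated figure for this sub-analysis, so there is none to reproduce. The check has three parts.

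**1. What the 2 L line means for each prior limit.** Let L be the prior limit and W the average week-6 intake. A patient is in the high group when W > 2, that is, when the increase W − L exceeds 2 − L.

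| Prior limit L | Increase needed to be classed above 2 L |
|---|---|
| 1 L | 2 − 1 = 1.0 L |
| 1.5 L | 2 − 1.5 = 0.5 L |
| 2 L (upper end of the 1.5 to 2 L row) | 2 − 2 = 0 L |

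The ordering can therefore be reversed:

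- 1 L to 1.8 L is +0.8 L (+80%) and is classed low. 2 L to 2.1 L is +0.1 L (+5%) and is classed high.
- With single-valued table rows only: 1 L to 1.9 L is +0.9 L and low; 1.5 L to 2.1 L is +0.6 L and high.
- W = 2 L exactly satisfies neither condition.

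**2. How far the split depends on the prior limit.** The documents give neither the mix of prior limits nor the distribution of week-6 intake, so only a range under assumptions is possible. Simulation of 400,000 patients per scenario:

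W = 1.9 + b × (L − mean of L) + normal error.

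Every input is an assumption: L = 1, 1.5 or 2 L in shares 10/60/30%, 20/40/40% or 5/80/15%; error SD 0.3 or 0.5 L; b = 0 (intake unrelated to the prior limit), 0.5, or 1 (intake follows it one for one). The share of variance is the squared correlation between L and membership of the high group.

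| b | Share of variance of the split explained by L |
|---|---|
| 0 | 0% |
| 0.5 | 3% to 18% |
| 1 | 9% to 44% |

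Across all scenarios:

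- Mean increase is +0.45 to +0.81 L in the high group and −0.04 to +0.20 L in the low group.
- 44% to 80% of the low group still drank more than their prior limit.
- Grouping by an increase above 0.5 L (an assumed cut) agrees with the 2 L split in 68% to 94% of patients, so 6% to 32% would change group.

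**3. Whether change from the limit must replace absolute intake.** Suppose the model is Y = a + c(W − L) + dL. Rearranged, it is Y = a + cW + (d − c)L. The coefficient c is the same in both forms. Once L is in the model linearly, using change or absolute intake makes no difference to the slope of interest; what matters is adjusting for L. This is useful because W − L has no single value for a range such as 1.5 to 2 L or for the row of other arrangements, whereas a category for prior management can be entered for everyone.

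**The case against.** The strongest defence has four parts.

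- **The split carries real information on increase.** This stands: mean increase was larger above 2 L in every scenario tried. A 2 L line is a reasonable description of intake level if it is labelled as that.
- **A reader might infer that the two groups mostly reproduce the earlier prescription.** The documents do not support this. They give no distribution of limits or intakes. High shares arise when intake is assumed to follow the prior limit closely, and liberal intake as desired gives no basis for that assumption. Even with b = 1 the prior limit explained at most 44% of the split, and with b = 0 it explained none.
- **There are partial safeguards.** Section 4 requires patient characteristics to be shown as in 3.7, so imbalance in prior management, BMI and NT-proBNP would be visible. SAP 3.12 allows baseline adjustment of the Cox models if unexpected differences appear. So it would be wrong to say that no endpoint can be adjusted. Neither safeguard changes the KCCQ-OSS model.
- **The weight is low.** This is one non-randomised contrast outside the hierarchical testing of SAP 3.3. Analysis 1 keeps the randomised comparison in the same prior-restriction subgroup.

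What remains is the mismatch between aim and grouping, the unadjusted KCCQ-OSS comparison of self-selected groups, and the word effect. In the rebuttal letter in the Protocol (major concern 7) the sponsor already accepts that a per-protocol analysis is biased and that actual intake is uncertain. Analysis 2 rests on the same week-6 report without that caution.

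**Conclusion.** The point holds as a minor one. As written, Analysis 2 gives a confounded contrast of week-6 intake level under the name of an effect of increased intake. Three facts follow from the text alone: the prior limit does not enter the grouping, patients can be ordered opposite to their increase, and an average of exactly 2 L is unassigned.

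The size of the distortion cannot be derived. The 0% to 44% range for the prior limit rests entirely on the assumed mixes, slopes and error SDs above, and it says nothing about the size or direction of bias in KCCQ-OSS or safety endpoints. Confounding by thirst, body size or congestion is plausible but not quantified in the documents. The primary analysis and Analysis 1 are not touched.

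**What to change.** In SAP section 4, for Analysis 2:

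1. Model average week-6 intake as a continuous term.
2. Add prior fluid-management category as a covariate. Keep it categorical, because range and other entries have no single value.
3. Adjust also for the baseline score of the outcome, baseline TDS-HF, BMI, diuretic dosage and NT-proBNP. All are already planned (SAP 3.7 and 3.10.3).
4. Keep the 2 L split as description only, and state which group takes an average of exactly 2 L.
5. Reword aim 2 as the association with week-6 intake level, and leave the causal comparison to Analysis 1.

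**Cost:** SAP wording and a slightly larger model in a subset of one arm; no new data. Two limits remain. The prescribed limit is only a proxy for what patients drank before, since no measured baseline intake is listed. Adjustment covers only the listed variables, and follow-up for events starts before week 6, so the result stays observational.

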3.11. Analysis of the secondary outcomes

For the secondary parameters thirst distress, as assessed with the TDS-HF, and QoL at 3 months after randomisation, as assessed with the KCCQ-CSS, each of the KCCQ domains and the EQ-5D-5L, a similar approach as for the primary study parameters will be adopted.

The difference between groups in proportion of patients with clinically meaningful changes (defined as a difference of 5 points compared to baseline) in KCCQ-OSS and KCCQ-CSS (8, 10) and the percentage of events (death, all-cause hospitalisations, the need for iv-loop diuretics and acute kidney injury) will be tested with Chi-square or Fisher exact test, whichever appropriate. The

difference in between groups patient reported fluid intake will be analysed with a Students' t test or Mann-Whitney U test, whichever appropriate.

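### Fluid-management sub-analyses 2 and 3 have no week-6 landmark, so events before week 6 are lost from, or moved between, the liberal-intake groups

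*SAP*

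**What the plan says.** SAP section 4, under the heading on change of fluid management, plans three analyses of patients who already had a fluid restriction before randomisation.

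- Sub-analysis 1 compares the randomised arms in this population.
- Sub-analysis 2 takes only the liberal arm: "Patients will be divided into two groups for analysis based on their average fluid intake at week 6 (less or more than 2L").
- Sub-analysis 3 has three groups. Group (a) is "Randomised to fluid restriction", with no further condition. Groups (b) and (c) are liberal patients below and above 2 L at week 6; (c) is "Randomised to liberal fluid intake and a fluid intake of more than 2L based on their average fluid intake at week 6".

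Aim 2 is worded causally: "To investigate the effect of increased fluid intake in the subgroup of patients who were prescribed a fluid restriction at baseline". For methods, "The analysis on the primary, (key) secondary and exploratory endpoints will be performed as described in" sections 3.10 to 3.12. Section 3.11 says that "the percentage of events (death, all-cause hospitalisations, the need for iv-loop diuretics and acute kidney injury) will be tested" between groups. In section 3.12 the top tier of the win ratio is "Death is worse than no death", and time-to-event outcomes use a Cox model.

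None of these sections gives a landmark, delayed entry, or a rule for a patient without a week-6 report. The imputation in section 3.10.4 covers KCCQ scores and auxiliary variables, not intake as a grouping variable. Section 3.12 does not state when the six months start.

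**The concern.** Two separate problems follow from grouping on a week-6 value while counting events over the whole six months.

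1. **Unequal entry (sub-analysis 3).** A liberal patient must survive and report in week 6 to be placed in (b) or (c). A restriction patient needs neither to be placed in (a). Early liberal deaths therefore drop out and early restriction deaths remain. This is the usual immortal-time asymmetry. Sub-analysis 2 does not have it, because both of its groups need the report.

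2. **Exposure measured after the event (sub-analyses 2 and 3).** An event before week 6 is set against an intake recorded afterwards and chosen by the patient. If an early hospitalisation changes later drinking, the patient moves between the under-2 L and over-2 L groups, taking the event along, with no report missing.

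What is at stake is how the results are read. The over-2 L group is where readers will look for the safety of drinking more, and the wording of Aim 2 invites them to read it as a treatment effect.

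**Working it through.** **Inputs from the documents.** The plan gives no figure for these sub-analyses. Its trial-wide sample size (SAP section 2.6) reproduces: residual SD = 20 × √(1 − 0.88²) = 9.50; n per arm = 2 × (1.96 + 0.8416)² × 9.50² / 2.5² = 226.7, so 227 per arm and 454 in total; 454 / 0.9 = 504.4, and 506 are planned, or 253 per arm.

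**Assumptions, because the documents give no event rates.** No true effect; constant hazard; 26 weeks of follow-up from randomisation; six-month mortality m of 2%, 5% or 10%; 50-100% of 253 patients with a prior restriction, so n = 127 to 253 per group.

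**Step 1: deaths lost from the liberal arm.** The risk in pooled (b)+(c), given survival to week 6, is 1 − (1 − m)^(20/26). In (a) it is m.

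| m | Risk in (b)+(c) | Risk ratio | Win ratio, death tier alone |
|---|---|---|---|
| 2% | 1.54% | 0.771 | 1.30 |
| 5% | 3.87% | 0.774 | 1.31 |
| 10% | 7.78% | 0.778 | 1.32 |

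A simulated Cox model under the null gives hazard ratios of 0.77 (3% mortality) and 0.74 (10%) without a landmark, and 1.01 and 0.97 with one (simulation standard error of the log hazard ratio 0.04 and 0.02).

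**Step 2: number of deaths and sampling error.** Expected deaths in weeks 0-6 in (a) = n × [1 − (1 − m)^(6/26)]: 0.6 to 1.2 at 2%, and 1.5 to 3.0 at 5%. At 2%, the chance that no patient in a group of this size dies before week 6 is 55% (n = 127) to 31% (n = 253). The standard error of the log death risk ratio, √(2(1 − m)/(nm)), is 0.88 (2%, n = 127) to 0.39 (5%, n = 253). The bias on the log scale is about −0.26, so it is 0.26/0.88 = 0.3 to 0.26/0.39 = 0.7 of one standard error.

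**Step 3: composite, only early deaths lost.** Assumed six-month risks of death / HF hospitalisation / iv diuretics / other hospitalisation, taken as independent: A 2/3/3/12%, B 5/6/5/15%, C 2/6/5/15%. With s the probability of no non-fatal event, the risk is 1 − s(1 − m) in (a) and R = 1 − s(1 − m)^(20/26) in (b)+(c).

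- A: s = 0.828; 0.1848 / 0.1886 = 0.98
- B: s = 0.759; 0.2703 / 0.2789 = 0.97
- C: s = 0.759; 0.2527 / 0.2561 = 0.99

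In simulation the four-tier win ratio is 1.02 to 1.05. For comparison, the standard error of the log composite risk ratio is 0.26 (risk 0.19, n = 127) to 0.14 (risk 0.28, n = 253).

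**Step 4: movement between (b) and (c).** Assume a 50/50 split at 2 L and no report missing except through death. Let e = 1 − s^(6/26) be the chance of an early non-fatal event (A 0.0426, B 0.0616), and let a share f of over-2 L patients with such an event move below 2 L. Then the risk is (R − fe)/(1 − fe) in (c) and (R + fe)/(1 + fe) in (b).

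| Scenario, f | (c) versus (a) | (b) versus (a) |
|---|---|---|
| A, 25% | 0.1760/0.1886 = 0.93 | 0.1934/0.1886 = 1.03 |
| B, 25% | 0.2589/0.2789 = 0.93 | 0.2814/0.2789 = 1.01 |
| A, 50% | 0.1670/0.1886 = 0.89 | 0.2018/0.1886 = 1.07 |
| B, 50% | 0.2471/0.2789 = 0.89 | 0.2921/0.2789 = 1.05 |

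With no true effect, the two liberal groups depart from (a) in opposite directions.

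**The case against.** The strongest reply is that little depends on this. These are supplementary analyses, sub-analysis 1 gives the randomised comparison in the same population, and SAP section 3.3 treats secondary endpoints beyond the key one as supportive. The exclusion of NYHA class IV and of life expectancy under six months points to low mortality. The death bias is below one standard error at 2-5% mortality, and splitting the liberal arm makes the comparison less precise still. All of this stands and sets the severity.

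It is also fair that steps 1 to 3 pool (b) and (c), a contrast that the SAP does not name, and that the 25-50% movement in step 4 has no source in the documents. Those figures show direction and order of size; they are not forecasts.

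A reader might infer that the over-2 L group is bound to look safer than restriction. The documents do not support that. Losing early deaths favours the pooled liberal groups, but (c) versus (a) also depends on who moves across 2 L and on confounding by self-chosen intake, which could act either way. A reader might also infer that the trial's safety result is compromised. It is not, because the randomised arms are compared without any week-6 condition.

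The reply does not remove the asymmetry. It follows directly from the group definitions, even though the SAP never says in words that early liberal deaths are excluded.

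**Conclusion.** The concern holds, at low severity: worth correcting, but no main conclusion rests on it. As written, sub-analysis 3 treats early deaths and missing reports differently by arm, and sub-analyses 2 and 3 both count events that precede the intake defining the groups.

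Under no true effect, constant hazard and follow-up from randomisation, the pooled death risk ratio is about 0.77-0.78 at 2-10% mortality. The pooled composite is 0.97-0.99. With assumed movement of 25-50%, the composite is about 0.89-0.93 for (c) versus (a) and 1.01-1.07 for (b) versus (a). Every event rate and movement share is an assumption. The net direction for (c) versus (a) is not known.

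**What to change.** Change SAP section 4 only.

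1. **Event endpoints, sub-analyses 2 and 3.** Set one landmark on a fixed study day at the end of the seven-day week-6 report. Include in every group, (a) included, only patients who are alive, in follow-up and have a week-6 report on that day. Count only later events.
2. **Three-month KCCQ, TDS-HF and EQ-5D-5L, sub-analysis 3.** Apply the same inclusion condition to all three groups.
3. **Reporting.** List the excluded patients and their events before the landmark by randomised arm. State how many reported days are needed to compute an average.
4. **Wording.** Recast Aim 2 as a non-randomised association between week-6 intake and outcome, and refer safety conclusions for this population to sub-analysis 1.

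No new data are needed, because section 3.8 already uses a seven-day week-6 report in the restriction arm. The cost is the loss of the first 6 to 7 of 26 weeks (23-27% of follow-up) from the event analyses in these two sub-analyses. Requiring a report brings some selection of its own, and group (a) is then no longer everyone randomised to restriction. Confounding by self-chosen intake remains.
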